5.2 Discussion of Study Design

After completing the 24-week double-blind Treatment Period in 1 of the 3 core studies, an estimated 1880 subjects will be randomized to 1 of 2 open-label treatment groups:

- 1. OKZ 64 mg q4w: SC injection of OKZ 64 mg q4w + MTX
- 2. OKZ 64 mg q2w: SC injection of OKZ 64 mg q2w + MTX

Subjects will be randomized based on the treatment received in the core studies. Subjects who received OKZ (q2w or q4w) in the core study in which they participated (including subjects who received placebo in Study CL04041025 and were re-randomized to OKZ at Week 16) will receive the same OKZ treatment regimen in the OLE study. Subjects who received placebo (Study CL04041022 and Study CL04041023) or adalimumab (Study CL04041023) in the core study in which they participated will be randomized in a 1:1 ratio to OKZ 64 mg q2w or OKZ 64 mg q4w regimens in the OLE study.

The total duration of OKZ treatment will depend on the subject's treatment assignment in the core studies:

- Subjects randomized to OKZ in the 3 core studies (CL04041022, CL04041023, and CL04041025) will complete 106 total weeks of treatment with OKZ.
- Subjects randomized to placebo in Study CL04041022 and to placebo or adalimumab in Study CL04041023 will complete 82 total weeks of treatment with OKZ.
- Subjects randomized to placebo in Study CL04041025 will transition to OKZ at Week 16 and complete 8 weeks of double-blind treatment with OKZ during the core study; these subjects will complete 90 total weeks of treatment with OKZ.

Subcutaneous injections of OKZ 64 mg will be administered q2w or q4w throughout the open-label Treatment Period, and all subjects (and their caregivers, if applicable) will be trained at Visit 1 (OLE Baseline/Week 24) to administer OKZ (see Section 6.8). Administration of study treatment will be observed by study site staff during the first 2 scheduled visits (Visit 1 [Week 24] and Visit 2 [Week 26] for subjects receiving OKZ 64 mg q2w, and Visit 1 [Week 24] and Visit 3 [Week 28] for subjects receiving OKZ 64 mg q4w). Detailed guidance on study treatment administration procedures will be provided in the Pharmacy Manual and Subject Leaflet.

For the first 12 weeks (up to Visit 4 [Week 36]) of the open-label Treatment Period, all subjects will be required to remain on a stable dose of background MTX at 15 to 25 mg/week (or ≥10 mg/week if there is documented intolerance to higher doses) with a stable route of

administration (oral, SC, or intramuscular [IM]), and subjects who were assigned rescue medication (sulfasalazine and/or hydroxychloroquine) in the core studies will be asked to continue these medications without a change in dose. Background therapy may be adjusted only for safety reasons according to Investigator discretion before Visit 4 (Week 36) of the OLE study.

Throughout the study, concomitant treatment with folic acid ≥ 5 mg per week or equivalent is required for all subjects.

The Investigator may, at their discretion and based on local practice, adjust therapy after Visit 4 (Week 36) (see Section 6.13.3), which may include adjustments to background therapy (i.e., MTX for all subjects, sulfasalazine and/or hydroxychloroquine for subjects assigned rescue medication in the core studies, and oral corticosteroids [if applicable]), parenteral corticosteroids, and modification of NSAIDs.

Dose tapering of oral corticosteroids or NSAIDs is permitted according to Investigator discretion before Visit 4 (Week 36) (see Section 6.13.3).

Subjects will return to the study site periodically for safety and response assessments as per Table 1. Adverse events will be assessed throughout the study period and evaluated using the CTCAE version 4.0.

The last dose of open-label study treatment in the OLE study will be administered at Week 104. After completion of the 82-week, open-label Treatment Period, subjects will enter the 20-week Safety Follow-Up Period. During the Safety Follow-Up Period, subjects will return for 3 visits at +4, +8, and +22 weeks after the last dose of study treatment.

Subjects who discontinue study treatment prematurely will be required to come to Visit 10 (EoT/Week 106) 2 weeks after the last dose of the study treatment for scheduled assessments. These subjects will subsequently be followed for an additional 20 weeks (i.e., 22 weeks after the final dose of study treatment) for a Safety Follow-Up Period.

There will be ongoing monitoring of safety events, including laboratory findings, by R-Pharm International or its designee. In addition, safety will be assessed throughout the study by an independent Data Safety Monitoring Board (DSMB) (see Section 7.4.4 for further details).

5.2.1 Cardiovascular Risk Assessment

The RA population is known to have an increased risk of cardiovascular (CV) events. In order to fully assess the CV risks associated with OKZ, the following approach will be implemented:

- Potential MACE will be adjudicated by an independent Cardiovascular
 Adjudication Committee (CVAC) according to a predefined charter. The charter
 will define the criteria, data, and source documentation required to adjudicate all
 MACE.
- 2. Baseline (of the core study) CV risks including individual risk factors (e.g., tobacco use, presence of hypertension, diabetes mellitus, and lipid profile) will be assessed.
- 3. Known CV risk factors will be monitored and assessed to detect any trends over long-term exposure. A CV risk assessment will be performed at OLE Baseline and at Visits 6 (Week 52), 8 (Week 76), and 10 (EoT/Week 106). The CV risk assessment includes:
 - Alcohol use with evaluation of average number of drinks consumed weekly
 - Tobacco use with evaluation of average number of tobacco products consumed daily
 - Central obesity
 - Use of any lipid-lowering medication or any other CV agents
 - Prior history of CV events and diabetes
 - Family history of premature CV disease (age of diagnosis <55 years for males and <65 years for females)
 - Other risks

Cardiovascular risk assessment data will be provided to the CVAC for review and adjudication of MACE (see Section 7.4.4.2).

5.2.2 Safety Follow-up Assessments

Given the long half-life of OKZ (approximately 31 days), subjects will be followed up for approximately 5 OKZ half-lives (i.e., 22 weeks) after the final dose of study treatment.

For subjects remaining on randomized therapy until the last scheduled dose of study treatment, Visit 10 (EoT Visit) will be performed at Week 106 and extended Safety Follow-Up procedures will be performed at visits scheduled +4, +8, and +22 weeks after the last dose of study treatment (i.e., Visits SFU-1 [Week 108], SFU-2 [Week 112], and SFU-3 [Week 126], respectively).

Subjects who discontinue treatment early require a full safety assessment at Visit 10 (EoT/Week 106) (see Section 5.4.2), which will take place 2 weeks after the last study

treatment administration. These subjects will subsequently be followed for an additional 20 weeks (i.e., 22 weeks after the final dose of study treatment) during a Safety Follow-Up Period (see Section 5.4.3).

All subjects will be reminded of study contact information to report potential SAEs and are to inform the Investigator if they experience such events during the Safety Follow-Up Period (Section 7.4.5.4).

5.3 Selection of Study Population

The study population will consist of subjects with moderately to severely active RA who previously completed 24 weeks of double-blind treatment in one of the core CREDO studies.

This is an international study, and it is expected that approximately 1880 subjects will be randomized at approximately 250 sites across Russia, Belarus, the US, Europe, UK, Asia, and Latin America.

5.3.1 Inclusion Criteria

Subjects may be enrolled in the study only if they meet all of the following criteria:

- 1. Subject must be willing and able to sign informed consent
- 2. Subject must have completed the 24-week double-blind Treatment Period in 1 of the 3 core studies (CL04041022, CL04041023, or CL04041025).
- 3. Subject must have maintained their stable dose (and route) of MTX 15 to 25 mg/week (or ≥10 mg/week if there is documented intolerance to higher doses) during the core study and plan to maintain the same dose and route of administration for ≥12 additional weeks.
- 4. Subjects must be willing to take folic acid or equivalent throughout the study.

5.3.2 Exclusion Criteria

Subjects who meet any of the following criteria will not be eligible for the study:

- 1. Subject with any medically important condition in the core study (e.g., clinically significant laboratory values, frequent AEs or SAEs, infection SAEs, and/or other concurrent severe and/or uncontrolled medical condition) which would make this subject unsuitable for inclusion in the OLE study in the Investigator's judgement.
- 2. Subject has evidence of active TB
- 3. Subject with a positive or repeated indeterminate interferon-gamma release assay (IGRA) result at Week 22 of the core study

- Subjects may be enrolled in the OLE study if they fulfill all 3 of the following criteria prior to the first dose of study treatment:
 - a. Active TB is ruled out by a certified TB specialist or pulmonologist who is familiar with diagnosing and treating TB (as acceptable per local practice);
 - b. The subject starts prophylaxis for latent TB infection (LTBI) according to country-specific/Centers for Disease Control and Prevention (CDC) guidelines (see Appendix 4 [Section 13.4]) (treatment with isoniazid for 6 months is not an appropriate prophylactic regime for this study and it should not be used); and
 - c. The subject is willing to complete the entire course of recommended LTBI therapy (see Appendix 4 [Section 13.4]).
- 4. Subject has planned surgery during the first 12 weeks of the OLE study
- 5. Female subjects who are pregnant or lactating, or who are planning to become pregnant during the study or within 6 months of the last dose of study treatment
- 6. Female subjects of childbearing potential (unless permanent cessation of menstrual periods, determined retrospectively after a woman has experienced 12 months of natural amenorrhea as defined by the amenorrhea with underlying status [e.g., correlative age] or 6 months of natural amenorrhea with documented serum follicle-stimulating hormone levels >40 mIU/mL and estradiol <20 pg/mL) who are not willing to use a highly effective method of contraception during the study and for at least 6 months after the last administration of study treatment

OR

Male subjects with partners of childbearing potential not willing to use a highly effective method of contraception during the study and for at least 3 months after the last administration of study treatment.

Highly effective contraception is defined as:

- Female sterilization surgery: hysterectomy, surgical bilateral oophorectomy (with or without hysterectomy) or tubal ligation at least 6 weeks prior to the first dose of study treatment in the core study
 - In the case of oophorectomy alone, only when the reproductive status of the woman has been confirmed by documented follow-up hormone level assessment

- Total abstinence if it is the preferred and constant lifestyle of the subject. Thus, periodic abstinence such as ovulation, symptothermal, postovulation, calendar methods, and withdrawal are not acceptable methods of contraception.
- Male sterilization surgery: at least 6 months prior to the first dose of study treatment in the core study (with the appropriate postvasectomy documentation of the absence of sperm in the ejaculate). For female subjects, the vasectomized male should be the only partner.
- Placement of established intrauterine device (IUD): IUD copper or IUD with progesterone
- Barrier method (condom and intravaginal spermicide, cervical caps with spermicide, or diaphragm with spermicide) in combination with the following: established oral, injected, or implanted hormone methods of contraception or contraceptive patch
- 7. Subject is unwilling or unable to follow the procedures outlined in the protocol
- 8. Other medical or psychiatric conditions, or laboratory abnormalities that may increase the potential risk associated with study participation and administration of the study treatment, or that may affect study results interpretation and, as per Investigator's judgement, make the subject ineligible.

5.3.3 Subject Restrictions

The following restrictions may affect a subject's ability to participate in this study:

- Availability to attend visits according to the protocol within the allowed window period specified in Table 1
- Ability to perform self-administration of study treatment, availability of caregiver to administer study treatment, or ability to visit study site to administer study treatment
- Concomitant medication restrictions as described in Section 6.13
- Fasting (water and concomitant medications are permitted) for at least 9 hours prior to all study visits

The Investigator (or designee) should review these restrictions with the subject when assessing eligibility to determine any potential challenges in the subject's ability to comply with the protocol. Subjects not able to comply with the above mentioned restrictions should not be enrolled into the study.

5.3.4 Premature Subject Withdrawal

All subjects are free to withdraw from participation in the study at any time, for any reason, specified or unspecified, and without prejudice to further treatment.

If premature withdrawal occurs for any reason, the Investigator must make every effort to determine the primary reason for a subject's premature withdrawal from the study and record this information on the source documents and appropriate electronic case report form (eCRF).

Subjects will be completely withdrawn from study treatment and all assessments in the following cases:

- Withdrawal of informed consent
- Death of subject
- Subject lost to follow-up
 - Note: If the subject is lost to follow-up, the Investigator should attempt to contact
 the subject until the last scheduled Safety Follow-Up Visit. The date of study
 termination for the subject is the date of last contact with subject.

If the subject withdraws from the study and withdraws consent for disclosure of future information, no further evaluations should be performed, and no additional data should be collected. R-Pharm International may retain and continue to use any data collected before such withdrawal of consent.

Investigators are strongly encouraged to discuss the withdrawal of a subject with R-Pharm International or R-Pharm International's designee in advance whenever possible.

5.4 Study Procedures

Every effort should be made to ensure that the protocol-required tests and procedures are completed as described. However, it is anticipated that from time to time there may be circumstances outside of the control of the Investigator that may make it unfeasible to perform the test. In these cases, the Investigator will take all steps necessary to ensure the safety and wellbeing of the subject.

The timing for all study visits during the open-label Treatment Period is relative to OLE Baseline. The timing for all study visits during the Safety Follow-Up Period (Visits SFU-1, SFU-2, and SFU-3) is relative to the last dose of study treatment (+4, +8, and +22 weeks, respectively).

As much as possible, subjects should be seen for all scheduled visits on the designated day. There is a ± 5 day visit window for all study visits with the exception of the 3 Safety Follow-Up Visits (± 7 days).

If a subject misses a visit and comes for an Unscheduled Visit, procedures for the assessment of safety and efficacy should be performed according to the most recent visit that was omitted. When a protocol-required procedure cannot be performed, the Investigator will document in the source documents the reason for this and any corrective and preventive actions that he/she has taken to ensure that normal processes are adhered to as soon as possible. The study team should be informed of these incidents in a timely fashion.

The assessments to be performed at each study visit should be conducted in the standard order listed below. At all visits, the PRO questionnaires should be performed first, prior to any discussion between the subject and study site staff.

The standard order should be:

- All PRO questionnaires (prior to any discussion between the subject and study site staff)
- Patient Global Assessment of Disease Activity (Visual Analog Scale [VAS])
- Patient Assessment of Pain (VAS)
- HAQ-DI
- SF-36
- EQ-5D
- FACIT-Fatigue
- WPS-RA (this PRO is conducted by study site staff after the subject completes all other PROs)
- Joint counts (Independent Joint Assessment)
- Soliciting of AE information
- Physician Global Assessment (VAS)
- All other assessments

In the following sections, assessments are listed for each visit according to this order.

5.4.1 Open-label Treatment Period Visits: Visit 1 (OLE Baseline/Week 24) through Visit 9 (Week 88)

5.4.1.1 Visit 1 (OLE Baseline/Week 24)

Written informed consent for the OLE study must be obtained prior to the performance of any protocol-specific procedures at Visit 1 (OLE Baseline/Week 24). The Investigator at each study site will ensure that each subject has been provided with full and adequate oral and written information about the nature, purpose, and available details of possible risks and benefits of the study.

Subjects must also be notified that they are free to discontinue from the study treatment or the whole study at any time. The Investigator will discuss with the subject the importance of attending all scheduled study site visits, including the EoT Visit and Safety Follow-Up Visits, regardless of whether the subject chooses to discontinue from the study treatment, or not. The subject should be given the opportunity to ask questions and allowed adequate time to consider the written information provided. The Investigator must retain the original, signed informed consent form (ICF) for the study file. A copy of the signed ICF must be given to the subject. Once informed consent has been obtained, the subject's eligibility to enter the study will be verified in accordance with the inclusion and exclusion criteria (refer to Sections 5.3.1 and 5.3.2, respectively).

If a subject meets all study eligibility criteria, the Investigator will randomize the subject via the Interactive Web Response System (IWRS) to one of the two open-label treatment groups (see Section 5.2). Subjects will keep the same subject number that they were assigned during the core study.

Visit 1 (OLE Baseline/Week 24) in the OLE study is the same as the Visit 15 (EoT/Week 24) visit in the core CREDO studies. Any assessments specified for the OLE Baseline Visit that duplicate the assessments specified for Week 24 in the core studies should only be performed once.

In addition to obtaining subject informed consent, the following assessments should be performed:

- Check eligibility criteria.
- Randomize subject (Via IWRS)
- Administer Patient Global Assessment of Disease Activity (VAS) (see Section 7.1.3).
- Administer Patient Assessment of Pain (VAS) (see Section 7.1.4).
- Administer HAQ-DI (see Section 7.1.10.1).

- Administer SF-36, EQ-5D, FACIT-Fatigue, and WPS-RA (see Section 7.1.10).
- Perform joint counts (Independent Joint Assessment) (see Section 7.1.2).
- Joint assessor will be independent to the rest of the study team. An independent joint assessor, blinded to other study assessments as well as the dosing regimen, will be identified at each study site to perform the swollen joint count (SJC) and tender joint count (TJC). To ensure consistent joint evaluation throughout the study, individual subjects should be evaluated by the same joint assessor for all study visits whenever possible.
- Assess AEs/SAEs.
- Assess injection site reactions that have occurred since the previous injection (see Section 7.4.3.5).
- Administer Physician Global Assessment (VAS) (see Section 7.1.5).
- Record details of contraceptive history/status.
- Record concomitant medications and concomitant non-drug therapies.
- Administer TB risk questionnaire (see Section 7.4.9).
- Record height and weight (see Section 7.4.7.3).
- Record vital signs (see Section 7.4.7.2).
- BP and heart rate also need to be reassessed 1 and 2 hours postdose.
- Perform complete physical examination (see Section 7.4.7.1).
- Perform CV risk assessment (see Section 7.4.7.4).
- Perform 12-lead electrocardiogram (ECG) (see Section 7.4.7.4).
- Perform chest X-ray (see Section 7.4.7.6).
- Chest X-ray need not be conducted if performed and evaluated within 8 weeks prior to Visit 1 (OLE Baseline/Week 24), and if the films or images are available and included in the subject's source documents.
- Collect samples for international normalized ratio (INR), activated partial thromboplastin time (aPTT), and fibrinogen (see Section 7.4.6.1).
- Measure ESR (see Section 7.4.6.1).

- Collect sample to measure CRP level (see Section 7.4.6.1).
- Collect samples for lipid panel and CV risk panel (see Section 7.4.6.1).
- Collect samples for chemistry panel, hematology assessments, antinuclear antibodies (ANA), and double-stranded DNA (dsDNA) antibodies (see Section 7.4.6.1).
- Collect PK sample prior to the first dose of study treatment (see Section 7.2).
- Collect sample for analysis of ADAs (see Section 7.3).
- Perform urine pregnancy test for females of childbearing potential only.
- Perform urinalysis (see Section 7.4.6.1).
- Allocate study treatment through the IWRS.
- Distribute Subject Diary and train subjects to properly complete the Subject Diary (see Section 5.5).
- Perform training for study treatment preparation, storage, and administration (see Section 6.8).
- Administer study treatment.
- Study treatment will be administered by the subject (or caregiver, if applicable) at this
 visit, and the Investigator must observe this administration to ensure that proper
 procedures are followed
- Subcutaneous injections may be rotated among the thighs and abdomen.
- All subjects will remain at the study site for at least 2 hours after the injection to be assessed for onset of any systemic injection reactions.

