7.4.3 Adverse Events of Special Interest

The following safety concerns were identified as AESIs based upon either the safety data available to date (refer to the most recent version of the Investigator's Brochure) for OKZ or drug class-related events for a biologic IL-6 inhibitor:

- Infections (particularly serious infections), including TB and opportunistic infections
- Confirmed cases of active TB must also be recorded as an SAE.
- Malignancies
- The Investigator will be asked to provide relevant medical information/documentation (e.g., pathology/histology reports) on all malignancy cases, whether considered serious or not, as these cases will be recorded in the safety database.
- Elevation of blood lipids (e.g., hypercholesterolemia, blood cholesterol increased, blood triglycerides increased, hypertriglyceridemia, and elevation of LDL)
- Systemic injection reactions and hypersensitivity reactions, including anaphylaxis
- Refer to Appendix 3 (Section 13.3) for details on diagnosing anaphylaxis.
- GI perforation
- CV events
- Neutropenia, thrombocytopenia, leukocytopenia, and pancytopenia
- Hepatotoxicity
- The Investigator will be asked to provide relevant medical information/documentation (e.g., laboratory test results, including tests for viral hepatitis and, if performed, liver biopsy) on all hepatotoxicity cases, whether considered serious or not, as these cases will be recorded in the safety database (see Section 7.4.3.4).
- Injection site reactions

- Demyelination in peripheral or central nervous system
- Autoimmune disorders.

All of the events listed above will be analyzed as AESIs; some of these events are further detailed below.

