9.4.6.1 Adverse Events

All AEs will be analyzed in terms of descriptive statistics and qualitative analysis. Adverse events will be listed for each subject and summarized by SOC and PT according to the latest version of the MedDRA. In addition, summaries of AEs by severity (evaluated using the CTCAE version 4.0) and relationship to study treatment will be presented.

An AE will be defined as treatment-emergent in the OLE study if its onset date or worsening in severity is on or after the date of first administration of the OLE study treatment. In cases

where only partial information is available for the onset date of an AE, available date components will be used to determine treatment-emergent status; in the case of ambiguity, AEs will be considered treatment-emergent.

The following summaries of subject incidence and number of events will be presented by the treatment groups defined in Section 9.4:

- Overall summary of TEAEs
- Summary of TEAEs by SOC and PT
- Summary of serious TEAEs by SOC and PT
- Summary of TEAEs leading to death by SOC and PT (if applicable)
- Summary of treatment-emergent AESIs (as defined in Section 7.4.3) by SOC and PT
- Summary of (adjudicated) MACE and individual MACE components
- Summary of TEAEs by SOC, PT, and maximum severity
- Summary of drug-related TEAEs by SOC and PT
- Summary of TEAEs leading to early treatment discontinuation by SOC and PT
- Summary of the most common TEAEs by PT (≥5% in any treatment group)
- Summary of TEAEs by Standardized MedDRA Queries narrow terms

Safety/tolerability and AE data will be presented in individual listings.

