9.4.6.1.1 Analysis of Treatment-Emergent Adverse Event Rates per 100 Patient-years of Follow-up

Summaries of TEAEs occurring in subjects in the safety population of this OLE study will also be provided based on combined AE data from the core studies and the OLE study, attributing each TEAE to the last study treatment received at/before the AE onset. In other words, an AE will be defined as treatment-emergent under a given study treatment (OKZ 64 mg q4w, OKZ 64 mg q2w, placebo, or adalimumab) if AE's onset date is on or after the date of first dose the corresponding treatment and prior to initiation of the next study treatment, if any (e.g., OKZ after placebo or adalimumab). In order to account for differences in the duration of exposure and follow-up under each study treatment and across subjects, subject IRs and ERs will be summarized per 100 subject-years (SY) of follow-up (/100 SY) based on the OLE safety population and presented by study treatments as follows:

- i. OKZ 64 mg q4w: subjects receiving OKZ 64 mg q4w during the core study or OLE. Only those TEAEs that first occur or worsen in severity after the first administration of OKZ 64 mg q4w (either in the core or OLE study) will be counted.
- ii. OKZ 64 mg q2w: subjects receiving OKZ 64 mg q2w during the core study or OLE. Only those TEAEs that first occur or worsen in severity after the first administration of OKZ 64 mg q2w (either in the core or OLE study) will be counted.
- iii. Placebo: subjects receiving placebo during the core study. Only those TEAEs that first occur or worsen in severity after the first administration of placebo and prior to administration of OKZ will be counted. Subjects are considered as receiving placebo during the core study if they are receiving placebo as their overall study treatment, and not as monthly placebo injections administered to maintain the blind in the OKZ 64 mg q4w group.
- iv. Adalimumab: subjects receiving adalimumab as active control study treatment during the core study CL04041023. Only those TEAEs that first occur or worsen in severity after the first administration of adalimumab and prior to administration of OKZ will be included.

The following summaries will be provided:

- IRs (/100 SY) and ERs (/100 SY) for TEAEs overall and by SOC
- IRs (/100 SY) and ERs (/100 SY) for SAEs overall and by SOC and PT
- IRs (/100 SY) and ERs (/100 SY) for AESIs overall and by SOC and PT

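### In the combined core-plus-OLE rates, injection site reactions to blinding placebo injections are counted under OKZ q4w; the OLE-only tables are essentially unaffected

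*Combined protocol and SAP*

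**What the plan says.** Section 7.4.3 lists injection site reactions among the AESIs and adds: "All of the events listed above will be analyzed as AESIs". Section 9.4.6.1.1 then plans "IRs (/100 SY) and ERs (/100 SY) for AESIs overall and by SOC and PT" on core and OLE data together, with cumulative mean function (CMF) plots for AESIs.

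The attribution rule in that section works by regimen, "attributing each TEAE to the last study treatment received at/before the AE onset". For treatment (i), OKZ 64 mg q4w, events that start or worsen "after the first administration of OKZ 64 mg q4w (either in the core or OLE study) will be counted". Treatment (iii), placebo, is limited to subjects who had placebo as their overall treatment, "and not as monthly placebo injections administered to maintain the blind in the OKZ 64 mg q4w group". Section 9.4 makes the same exclusion when it defines the treatment groups.

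Under Section 5.2, subjects on OKZ in a core study "will receive the same OKZ treatment regimen in the OLE study". The OLE is open-label (Section 6.12), and its q4w regimen includes no placebo injections.

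Two further passages set the limits of the point. Section 9.4.6.1 defines an event for the OLE-only tables as "treatment-emergent in the OLE study if its onset date or worsening in severity is on or after the date of first administration" of OLE treatment. Section 5.4.1.1 tells the site at Visit 1 to "Assess injection site reactions that have occurred since the previous injection".

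**The concern.** Attribution by regimen suits systemic events, because OKZ exposure is continuous between q4w doses. It suits a local reaction less well, because the relevant exposure is the single injection at that site. A reaction where a blinding placebo was injected is kept out of the placebo column and falls into the OKZ q4w column. It adds an event without adding follow-up time. In the incidence rate it can also be a subject's first event and so shorten that subject's time at risk.

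From Week 24 the q4w regimen cannot produce such reactions. One q4w figure therefore mixes two injection schedules, and the q4w CMF for continuing subjects could change slope at Week 24 for a reason unrelated to OKZ.

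The comparison matters to this programme. Section 2.2.4 cites dose-dependent injection site reactions as one reason for dropping the 240 mg regimen, and keeps the lower monthly dose partly for a possible long-term safety advantage. If q2w produces more reactions than q4w, the rule would hide part of the difference.

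**Working it through.** The plan gives no injection site reaction rate for either regimen or for placebo injections, so there is no figure to reproduce. The check is a count of injections with the unknown risks varied.

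**Inputs from the documents**
- Last OLE dose at Week 104 (Section 5.1); first at Week 24 (Section 2.3).
- Blinding placebo given monthly to core q4w subjects (Sections 9.4 and 9.4.6.1.1).
- OKZ follow-up ends at last dose plus 155 days, or last contact if earlier (Section 9.4.6.1.1). 5 half-lives × 31 days = 155, which agrees.

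**Assumptions**
- Core injections every 2 weeks at Weeks 0 to 22. A monthly placebo alternating with q4w OKZ fits this, but Week 22 is stated only for adalimumab (Section 2.3).
- All doses taken; constant risk per injection; equal risk per OKZ injection on q2w and q4w.
- k = reaction risk per placebo injection divided by risk per OKZ injection.
- f = share of OLE q4w subjects who continue from core q4w; the rest are taken to start OKZ at Week 24. Neither k nor f is in the documents.

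**Injection counts for a continuing completer**

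| Regimen | Core | OLE | OKZ total | Placebo |
|---|---|---|---|---|
| q4w | 6 OKZ + 6 placebo | 21 | 27 | 6 |
| q2w | 12 OKZ | 41 | 53 | 0 |

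**Event rate.** The follow-up denominator is the same with or without the placebo-site reactions.
- Overstatement of the q4w rate = 6k/27 = 22% × k.
- Narrowing of the q2w minus q4w gap = 6k/(53 − 27) = 23% × k.
- Ratio q2w:q4w = 53/(27 + 6k), against 53/27 = 1.96 without them.

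| k | q4w rate overstated | Gap narrowed | Ratio |
|---|---|---|---|
| 0 | 0% | 0% | 1.96 |
| 0.1 | 2% | 2% | 1.92 |
| 0.25 | 6% | 6% | 1.86 |
| 0.5 | 11% | 12% | 1.77 |
| 1 | 22% | 23% | 1.61 |

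**Pooled q4w column.** Overstatement = 6fk/(27f + 21(1 − f)). At f = 0.5 this is 3k/24 = 12.5% × k: 3% at k = 0.25, 6% at k = 0.5 and 12.5% at k = 1.

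**Core period alone.** 6k/6 = 100% × k.

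**Incidence rate (first event).** Follow-up for a continuing completer is 104 × 7 + 155 = 883 days, or 2.42 years. With an illustrative 2% risk per OKZ injection, the q4w rate per 100 subject-years is 23.6 at k = 0, 25.2 at k = 0.25 and 30.4 at k = 1; q2w is 48.1.

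**OLE-only tables.** A reaction to a core injection starts before the first OLE dose, so it does not meet the Section 9.4.6.1 definition. The exceptions are a later worsening, or a partial onset date that defaults to treatment-emergent.

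**The case against.** The strongest reply is that this is a disclosed convention. The plan states twice that the blinding injections do not make a subject placebo, it attributes by regimen throughout, and it leaves further safety detail to the SAP (Section 9.4.6). The affected outputs are additional to the OLE tables. All analyses are descriptive, so no test or decision rule is affected. That stands and limits the weight of the point. But disclosure does not remove the mixture, and in a descriptive study the displayed rates are the evidence.

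A reader might infer from the Visit 1 instruction that placebo-site reactions enter the OLE results. The documents do not support this. The instruction is a collection step at a visit shared with the core Week 24 visit. Section 7.4.5 has core events recorded again in the OLE only if they worsen, and Section 9.4.6.1 requires onset or worsening from the first OLE dose.

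A reader might also take it as established that the q4w rate is too high and the regimen gap too small. That is not supported either. At k = 0 there is no effect, and the narrowing presumes that q2w exceeds q4w.

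A further objection concerns the remedy. Section 7.4.3.5 gives no time window, so assigning each reaction to the most recent injection would move a late reaction at an OKZ site to placebo and pull the q4w rate down. That is correct, and the fix allows for it.

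**Conclusion.** The point holds for the combined core-plus-OLE incidence rates, event rates and CMF plots of Section 9.4.6.1.1, and only there. Reactions that follow a blinding placebo injection in core q4w subjects are counted under OKZ q4w. If any occur, the combined q4w figure overstates the rate for the open-label q4w regimen, and any q2w excess looks smaller.

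The size cannot be fixed from the documents. For the q4w event rate it is 22% × k if every q4w subject continues from core q4w, so 2% to 22% for k from 0.1 to 1. It is 12.5% × k if half do. These figures rest on the inferred two-weekly core schedule, full dosing and constant risk per injection; the effect would be larger if reactions cluster early or subjects stop early. The change is worthwhile because it is cheap and concerns a named AESI. No formal conclusion of the study depends on it.

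**What to change.** In Section 9.4.6.1.1, for injection site reactions only:

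1. Show the OKZ q4w incidence rate, event rate and CMF separately for the core and OLE periods.
2. Put core q4w reactions whose most recent injection was a blinding placebo on a separate line, and give the q4w rate with and without them.
3. State a tie rule for reactions with unclear timing or late onset; for example, they stay under OKZ q4w in both versions.

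The regimen rule can stay as it is for all other events. The cost is a few table rows and a merge with the core injection records, whose level of detail cannot be checked from these documents. Some late reactions will still be misassigned, which is why both versions should be shown. If the merge proves impractical, the period split in step 1 alone isolates the affected part.
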